#### **Abstract**

Raynaud's phenomenon (RP) is a common vascular disorder that affects approximately 10% of the general population. RP is associated with significant morbidity that may include loss of the digits due to repeated episodes of vasospasm of the digital arteries in addition to significant impairment of quality of life. It is well known that cold exposure precipitates episodes of RP, but the mechanism for cold sensitivity is not known, and treatment of RP is not satisfactory to the subjects and their physicians.

Our goal in this proposal is to test the possibility that non invasive vagus nerve stimulation (nVNS) with gammaCore may be an effective and well tolerated therapy for RP. We will perform the first proof of concept human study to demonstrate the clinical efficacy and safety of nVNS using gammaCore in RP.

We anticipate at the conclusion of the proposed work that we will have gained fundamental understanding of the role of nVNS as a potential therapy for RP, a truly unmet medical need. If successful in demonstrating measurable local vasodilatory effects, we will proceed in a second phase of the study to evaluate the effects of gammaCore on RP associated with Scleroderma.

#### **RESEARCH PLAN**

#### A. SPECIFIC AIMS

Raynaud's phenomenon (RP) is characterized by repeated episodes of vasospasm that may lead to vascular injury and tissue ischemia. RP is classified as primary (PRP) or secondary (SRP) in the absence or presence of underlying autoimmune connective tissue disease, respectively. The exact cause of RP is undetermined and the current treatment modalities are largely unsatisfactory and frequently associated with significant side effects. In this proposal, we aim to investigate the efficacy of nVNS using gammaCore in PRP subjects. nVNS using gammaCore has recently received clearance from the US FDA for acute cluster headache and migraine treatment in adults. RP is frequently associated with headaches, particularly migraine headaches. Indeed, migraine is a risk factor for development of RP with a pooled OR of 4.02 (95% CI 2.62 to 6.17) in six studies [1], suggesting vasospasm as a common pathogenic process.

## The Specific Sequential Aims of this application are as follows:

- Aim 1: Evaluate the clinical efficacy of gammaCore (16 subjects) vs sham device (16 subjects) in preventing vasospasm in 32 PRP subjects.
- Aim 2: Evaluate the clinical efficacy of gammaCore (16 subjects) vs sham device (16 subjects each) on Raynaud's symptoms and chronic PRP in 32 subjects with chronic PRP for four weeks using Raynaud's condition score.
- Aim 3: Observe response rates in an open label fashion after sham subjects are transitioned to gammaCore.

#### **B. BACKGROUND AND SCIENTIFIC SIGNIFICANCE**

[figure not shown]
Raynaud's phenomenon is classified as PRP in the absence of other vascular or connective tissue disease, or SRP if it is associated with connective tissue disease, like systemic sclerosis (SSc, Scleroderma). RP is a common disorder that is characterized by reversible vasospasm of the digits induced by cold exposure or emotional stress, which induces episodes of tri-phasic color changes of the digits with blanching, cyanosis, and rubor followed by numbness, pain and often-functional disability with a significant impact on the quality of subject's life. Moreover, RP can be associated with digital ulceration and autoamputation [2]. PRP affects up to 10% of the general population in the United States [2]. The etiology and pathogenesis of RP are incompletely understood.

Treatment of RP is not satisfactory in general, as current therapy employing calcium channel blockers and other vasodilators are frequently ineffective or not well tolerated, due to significant side effects [3].

Noninvasive evaluation of blood flow at the digits in RP. We use Infrared Thermography (IT), a technology that relies on evaluating the difference of skin temperature as a tool for dynamic evaluation of digital blood flow by creating temperature maps. IT has been validated as a tool to evaluate RP and assess response to therapeutic interventions [4,5], with a conclusion that IT is a sensitive test with high reproducibility [6-9]. Studies have shown that IT correlate with digital blood flow at baseline and after cold challenge test by using temperature evaluation [9]. IT is considered a cost and time-saving to use for the monitoring of perfusion changes in subjects with RP [9].

Non-invasive assessment of RP often incorporates local cold challenge to allow dynamic vascular assessment under conditions thought to simulate those responsible to for an attack of RP [7].

[figure not shown]
Figure 1: Captured images of Raynaud's attack by IT, blue color represents lower temperature of the skin compared to red. (From Non-invasive Methods of Assessing Raynaud's phenomenon by Murray and Pauling, Raynaud's phenomenon 2015)

#### D. APPROACH and METHODOLOGY

# 1. Assessment of digital blood flow in response to cold challenge test

We used FLIR thermography system (Wilsonville, OR) to evaluate blood flow in the digits in response to cold challenge test. The advantage of IT is that we can obtain dynamic assessment of blood flow in the hands as reflected by change in temperature in response to cold challenge tests, as well as the ability to obtain single point measurements. **Figure 2** shows dynamic changes in surrogate marker of blood flow as detected by thermal images during the three phases of active Raynaud's phenomena that we were able to reproduce by cold challenge test.

**Figure 2:** An illustrative example of dynamic changes in vascular perfusion that are detected by infrared thermography. A) Active vasospasm, B) spontaneous improvement in blood flow, C) Hyperemia. Blue-yellow regions indicate areas of lower perfusion compared to red regions.

#### 2. EXPERIMENTAL DESIGN

# Study population

We will consent 40 subjects with Raynaud's phenomenon seen previously at the University of Toledo Medical Center (UTMC). After meeting the screening requirements 32 subjects will be randomized 1:1 to sham device (16) or gammaCore device (16). The sample size calculation is based on the minimum recommended number of samples to detect a difference in the outcome of the intervention with a confidence level of 90%, and margin of error of 10%. Each individual will sign an informed consent that is approved by the IRB at UTMC before participating in this study. The research protocol will be explained in detail and in lay language to each subject. We will exclude subjects who currently smoke, subjects with digital ulcers, subjects who are less than 18 years of age, subjects with pulmonary hypertension, and subjects who are receiving vasodilators such PDE-5 inhibitors, prostacyclin, nitroglycerine, or other nitric oxide derivatives. Subjects who are using Calcium Channel Blockers (CCBs) will be allowed to continue their medication, however, should be on stable therapy at least 4

weeks prior to study initiation. We will also exclude pregnant women from these studies, which will be evaluated at screening with a urine dipstick pregnancy test. Subjects who have had neck surgery in the past year (i.e. carotid endarterectomy) or that have a carotid bruit, will be excluded as well. GammaCore device cannot be used in those that have a history of metallic device such as a stent, bone plate, or bone screw implanted at or near their neck. Any history or current evidence of any condition, therapy, or other circumstances which, in the opinion of the investigator, might pose an unacceptable risk to the subject (i.e. unable to comply with requirements of the trial, or likely to interfere with the subjects participation for the full duration of the trial).

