Week 4 (Open Label). Subjects will return for cold challenge test and bring device back with them. Subjects will have follow up image #2 taken and then be treated with their current sham or gammaCore -20 minutes prior to cold challenge (stimulation 2 minutes each side of the neck for a total of 4 minutes) and then at time -4 minutes (stimulation 2 minutes each side of the neck for a total of 4 minutes) performed by the subject and monitored by the investigator, or delegated study personnel) immediately before cold challenge. Using FLIR thermography to measure absolute temperature, DDD, and DDDI will be calculated from images of both hands taken at baseline, obtained by a video where images are captured at 1 min, 5 min, 10 min, 15 min and 20 minutes after cold challenge will be measured at the dorsum and digits 2nd-4th. Images measuring the absolute temperature, DDD, and DDDI at specific regions as well as the average of all regions will be generated as a surrogate marker of blood flow.

Following Week 4 cold challenge sham subjects will be placed on active treatment with gammaCore so that all subjects will be on open label active treatment at Week 4. All subjects will be retrained on proper usage and administration of gammaCore. Subjects will stimulate for 4 minutes (2 minutes each side of neck) twice a day, once in AM and once in the PM at least 8 hours apart, for a total of 8 minutes of stimulation daily. The diary from week 0 to 4 will be collected and subjects will be provided a new diary to continue recording the completion of stimulation and occurrences with the device, and Raynaud's symptoms and attacks. Subjects will continue their treatments with the gammaCore device and continue to refrain from medications prohibited while enrolled in the study.

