## Statistical analysis.

Comparisons between absolute temperature, DDD, and DDDI between subjects and visits will be made. Mean values and standard deviations of the measurements IT end points will be determined. Sequentially, the differences in the mean values of temperature after a baseline and in response to cold challenge will be calculated and categorized as greater or less than1.2-fold change from the baseline average. Also, we will measure absolute temperature, DDD, and DDDI across the 2nd-4th digits bilaterally. We will calculate the mean of all absolute temperatures, DDD, and DDDI values and rate of change, and use t-test to calculate P value. P value <0.05 will be considered statistically significant. We will use one-way ANOVA for the means will be used for statistical analysis. Statistical significance will be considered if P < 0.05.

Anticipated results and interpretation. We predict that these experiments will provide the first clinical evidence that nVNS with gammaCore may be an effective treatment in PRP, by demonstrating that the stimulation abrogates vasospasm that is classically induced by cold challenge in subjects with PRP.

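### The stated basis for 32 subjects (90% confidence, 10% margin of error) does not support detecting a difference between two arms of 16, and 32 cannot be derived from the inputs given

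*Combined protocol and SAP*

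**What the plan says.** The Study population section plans to consent 40 subjects and randomise 32, in a 1:1 ratio, to sham or gammaCore. It calls 32 the minimum recommended number "to detect a difference in the outcome of the intervention with a confidence level of 90%, and margin of error of 10" per cent. That sentence is the only sizing rationale in the document.

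The Specific Aims are comparisons between arms. Aim 1 is to "Evaluate the clinical efficacy of gammaCore (16 subjects) vs sham device (16 subjects) in preventing vasospasm in 32 PRP subjects". Aim 2 makes the same 16 v 16 comparison "in 32 subjects with chronic PRP for four weeks using Raynaud's condition score".

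The Statistical analysis section works mainly with means: "Comparisons between absolute temperature, DDD, and DDDI between subjects and visits will be made", and "We will calculate the mean of all absolute temperatures, DDD, and DDDI values and rate of change, and use t-test to calculate P value". It adds "We will use one-way ANOVA for the means will be used for statistical analysis" and sets the criterion "P value <0.05 will be considered statistically significant". It also sorts temperature differences into greater or less than a 1.2-fold change from the baseline average, which is a two-category outcome.

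The randomised comparison ends at Week 4: "Following Week 4 cold challenge sham subjects will be placed on active treatment with gammaCore".

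**The concern.** The sentence claims the ability to detect a difference but gives the inputs of a precision calculation. A calculation for detecting a difference between two arms needs an endpoint, a difference, an SD (or two proportions), a significance level and a power. The document supplies only P<0.05, in another section, and that does not match a 90% confidence level.

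At stake is how the result will be read. A reader is told that 32 is enough, yet nothing says how large a difference 16 v 16 can detect. A non-significant result then has no planned effect to be read against, and may be mistaken for evidence of no effect.

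**Working it through.** **Inputs from the document.** 32 randomised, 16 per arm; 40 consented; 90% confidence; 10% margin of error (Study population). P<0.05, sidedness not given; t-test and one-way ANOVA on means (Statistical analysis).

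**Assumed, because the document is silent.** The proportion p, two-sided testing, 80% power, and 14 per arm as an example of loss after randomisation.

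**1. Trying to reproduce 32.** The usual formula for these two inputs is n = z²p(1−p)/e², with z = 1.645 and e = 0.10.

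- p = 0.5: 1.645² × 0.25 / 0.01 = 67.6, so 68.
- p = 0.3: 57. p = 0.2: 44. p = 0.10: 25.

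The formula gives 32 only with inputs that the document does not state as sizing inputs:

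- p of about 0.137.
- p = 0.5 with a finite-population correction, n = n₀/(1+(n₀−1)/N), and a source population N of about 60: N = 59 gives 31.8 and N = 60 gives 32.05. The only relevant count in the section, 40 consented, gives 25.4.
- p = 0.10 inflated for 20% loss: 25/0.8 = 31.25, so 32.

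**2. Precision that 16 v 16 gives.** The 90% margin for a difference between two proportions is 1.645 × √(2p(1−p)/16).

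- p = 0.5: 1.645 × √(0.5/16) = 0.291, about 29 points.
- p = 0.137: 1.645 × √(2 × 0.137 × 0.863/16) = 0.200, about 20 points.

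So even the value of p that makes the one-sample formula return 32 leaves a between-arm margin of twice the stated 10 points. The reason is general: splitting n subjects into two halves and taking the difference doubles the standard error of the pooled proportion.

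**3. What 16 v 16 can detect for a mean.** The test is an unadjusted two-sample t-test, by the noncentral t distribution. One-way ANOVA on two arms is the same test.

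| Per arm | Two-sided level | Power | Detectable difference |
|---|---|---|---|
| 16 | 5% | 80% | 1.02 SD |
| 14 (assumed) | 5% | 80% | 1.10 SD |
| 16 | 5% | 90% | 1.18 SD |
| 16 | 10% | 80% | 0.90 SD |

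The 95% CI half-width with 16 per arm is t(0.975, 30) × √(2/16) = 2.042 × 0.354 = 0.72 SD.

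**4. Sensitivity to baseline adjustment.** None is specified. If the outcome correlated 0.5 or 0.7 with baseline (assumed values), the 1.02 SD would become about 0.89 or 0.73 SD.

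**5. Illustration only.** The document gives no expected effect. With 16 per arm at two-sided 5%, power is 28% for 0.5 SD and 59% for 0.8 SD.

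**The case against.** **The sentence may be loosely worded, with 90% meaning power.** That is possible. The calculation would still lack an effect size and an SD. At two-sided 5% the detectable difference would be about 1.18 SD, a figure that appears nowhere in the document.

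**Some combination of inputs does give 32.** This stands, as step 1 shows. The document even contains a 10% figure (prevalence of Raynaud's phenomenon) and an implied 20% loss (40 consented to 32 randomised). But neither is offered as a sizing input, the loss comes before randomisation, and prevalence is not an outcome proportion. So 32 is not derivable from the document, which is different from impossible.

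**A reader might infer that the trial needs 68 subjects, or is less than half the right size.** The documents do not support that. The 68 depends on p = 0.5, which no section states, and it would be the size for estimating one proportion, not for this comparison.

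**This is a proof-of-concept study, and a formal power calculation is not obligatory.** Agreed; 32 may be a sensible pragmatic size. The Study population section does not say that, however. It claims a calculated minimum for detecting a difference.

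**The SD figures do not fit every planned analysis.** Also right. They do not apply to the 1.2-fold category or to a paired or baseline-adjusted analysis. The Statistical analysis section does not say whether the t-test is between arms or paired; the between-arm reading is taken from Aims 1 and 2.

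**A non-significant result could still be read through an interval.** Yes, since means and SDs are planned. That is why the half-width belongs in the replacement text.

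**Conclusion.** The point holds as an unsupported justification, not as a proven shortage of subjects. The 90%/10% basis is a precision statement. It does not establish the ability to detect a difference between arms of 16, and it does not yield 32 from any stated input. Taken as the precision of a between-arm difference in proportions, it is missed by a factor of about two at p = 0.14 (20 points) and nearly three at p = 0.5 (29 points). The 90% level also disagrees with the P<0.05 criterion.

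The detectable difference of about 1.02 SD rests on an unadjusted, two-sided 5%, between-arm t-test with all 32 analysed. Whether that is adequate cannot be judged, because the documents give neither an expected effect nor an SD. It should be fixed, but it is no reason to change the number of subjects.

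**What to change.** Keep 32. Delete the 90% confidence and 10% margin of error, and put in their place wording such as:

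*The reason for choosing 32 subjects (16 per arm) is [sponsor to state, for example a proof-of-concept size]. For a continuous thermography measure compared between arms at a visit up to Week 4, with all 32 analysed, an unadjusted two-sided 5% t-test has 80% power for a difference of about 1.02 SD (about 1.10 SD if 14 per arm are analysed), and the 95% CI half-width is about 0.72 SD.*

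The limit of Week 4 follows from the move of sham subjects to gammaCore after that visit's cold challenge. If the comparison used for sizing is the 1.2-fold category or a baseline-adjusted analysis, restate the figures for that analysis. If an SD is available, give them in the measure's own units. Naming a single primary endpoint would also help, but it is a separate change that would alter the Statistical analysis section, and this fix does not depend on it.

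The cost is one rewritten passage, with no extra subjects, visits or procedures. The downside is that the stated basis becomes less favourable.

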# Thermography

We will use FLIR system to measure temperature and blood flow at the digits. After the cold challenge, subjects will place their hands on a setup of a carpet square measuring a length of 42.5 cm by 29.5 cm wide, placed backing side up (to reduce reflection), on a table with a grate resting on the carpet where the subject will be instructed to rest hands on. We will use 2 thresholds for use as screening when subjects do the first cold challenge without neurostimulation:

- 1. A Distal Dorsal Difference (DDD) >1°C at base line or
- 2. DDDI should > 20% at 5 min after the cold stress.

Subjects who meet the screening threshold of clinically meaningful change from baseline on the initial cold challenge will be enrolled into the study.

Week -4 (Screening). The screening visit where eligibility testing will be performed utilizing the cold challenge test, a baseline image will be taken, and physician verbal history interview performed. Subjects will begin to keep a diary of Raynaud's symptoms and number of attacks. Throughout the study, the diary will be collected at week 0, 4, 8, and 12. A diary will be provided at week -4, 0, 4, and 8. Beginning at week 0, stimulation time and occurrences with gammaCore device will be recorded in the diary along with at week 4. There is no use of gammaCore or sham at this point. Subjects continue their current standard of care treatments, except for medications prohibited while enrolled in the study.

Week 0 (Randomization). The first 32 subjects that meet screening criteria will be enrolled into the study. Diaries from Week -4 to Week 0 will be collected, and a new diary given. The 32 subjects will be randomized 1:1 to either sham device (16) or gammaCore device (16). At week 0 subjects will have a follow up image #1 taken and then be treated with sham or gammaCore -20 minutes prior to cold challenge. The first set of stimulation begins at -20 minutes (2 minutes on each side of the neck for a total of 4 minutes) and then at -4 minutes the second set of stimulation occurs (2 minutes on each side of the neck for a total of 4 minutes)

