performed by the subject, monitored by the investigator, or delegated study personnel immediately after cold challenge. Using FLIR thermography to measure absolute temperature, DDD, and DDDI will be calculated from images of both hands taken at baseline, obtained by a video where images are captured at 1 min, 5 min, 10 min, 15 min and 20 minutes after the cold challenge will be measured at the dorsum and digits 2nd-4th. Images measuring the absolute temperature, DDD, and DDDI at specific regions as well as the average of all regions will be generated as a surrogate marker of blood flow.

Prior to cold challenge subjects will be trained on proper usage and administration of sham and gammaCore devices. Subjects will stimulate for 4 minutes (2 minutes each side of neck) twice a day, once in AM and once in the PM, at least 8 hours apart\_for a total of 8 minutes of stimulation daily. Subjects will begin to log the completion of stimulation and occurrences with the device, and continue recording Raynaud's symptoms and number of attacks in the diary. Subjects will continue on their current treatments with sham or gammaCore device, and continue to refrain from medications prohibited while enrolled in the study.

Week 1. Subjects will return for observation of administration of treatment with any correction if necessary and confirm that subject is documenting RP symptoms and number of attacks as well as the use of the device in the diary.

Week 2. Subjects will be contacted via telephone for a follow up call to address any device stimulation issues, make corrections if necessary, as well as confirm that subject is documenting RP symptoms and number of attacks as well as the use of the device in the diary.

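### Pregnancy is an exclusion but is tested only at screening (Week -4), so the result is nominally 28 days old at randomisation, 56 at the Week 4 switch and 84 at the Week 8 challenge

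*Combined protocol and SAP*

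**What the plan says.** The Study population section of the combined protocol and SAP sets the exclusion and its only check: "We will also exclude pregnant women from these studies, which will be evaluated at screening with a urine dipstick pregnancy test".

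The Thermography section, which carries the visit-by-visit schedule, gives the label of screening to Week -4 alone. At that visit "eligibility testing will be performed utilizing the cold challenge test, a baseline image will be taken, and physician verbal history interview performed", and the same paragraph says that neither device is used yet.

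The later visits read as follows:

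- **Week 0.** "The first 32 subjects that meet screening criteria will be enrolled into the study". They are randomised, and then "At week 0 subjects will have a follow up image #1 taken and then be treated with sham or gammaCore". Twice-daily home use follows.
- **Week 1 and Week 2.** A visit, then a telephone call. Their stated content is device technique and diary completion.
- **Week 4.** "Subjects will have follow up image #2 taken and then be treated with their current sham or gammaCore". After the challenge, "sham subjects will be placed on active treatment with gammaCore so that all subjects will be on open label active treatment at Week 4".
- **Week 8.** Imaging, two stimulation sets, the cold challenge, and return of the device.

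None of these paragraphs mentions a second pregnancy test, and the text reviewed gives no contraception requirement and no rule for holding stimulation if a subject becomes pregnant.

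**The concern.** The sponsor chose to keep pregnant women out and thought the point worth a test. That test, however, falls at a visit where nobody is exposed, and none is scheduled on a day when the device is used. Staff who follow the schedule as written could randomise and stimulate a woman whose pregnancy began after Week -4. If she is in the sham arm, they could also start her on active gammaCore at Week 4. The switch carries no condition.

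Another eligibility restriction is carried forward: the Week 0 and Week 4 paragraphs remind subjects to stay off prohibited medications while in the study. Pregnancy has no such reminder. The Abstract describes the trial as the first proof-of-concept human study of efficacy and safety in this condition, which is a reason to keep the exclusion working once exposure begins.

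**Working it through.** The plan states no figure to reproduce. The check is calendar arithmetic plus a reading of each visit.

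**Inputs**

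- Only test: at screening (Study population), which is Week -4 (Thermography).
- Randomisation and first stimulation: Week 0. Switch of sham subjects: after the Week 4 challenge. Last stimulated challenge and device return: Week 8 (all Thermography).
- Home use: two sessions a day from Week 0 to Week 8 (Thermography).
- Numbers: 40 consented, 32 randomised, 16 per arm (Study population).

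**Age of the only test.** Age in days = 7 × (visit week + 4).

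| Event | Calculation | Age of test as planned | Age with the fix |
|---|---|---|---|
| Week 0, randomisation and first stimulation (both arms) | 7 × 4 | 28 days | same day |
| Week 4 challenge (both arms) and switch (16 sham subjects) | 7 × 8 | 56 days | same day |
| Week 8 challenge (both arms) | 7 × 12 | 84 days | same day |

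The days are nominal, because the protocol gives no visit windows. As planned, 84 days pass from the only test to the last scheduled device use. With tests at Weeks -4, 0, 4 and 8, the longest interval is 7 × 4 = 28 days.

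**Scheduled exposure after the only test.** From Week 0 there are 3 stimulated challenges with 3 × 2 = 6 clinic stimulation sets, and up to 56 × 2 = 112 home sessions. In the sham arm the home sessions split into 28 × 2 = 56 sham and 28 × 2 = 56 active. This counts exposure and is not a measure of risk.

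**Cost of the fix.** At most 3 × 32 = 96 dipsticks for the randomised subjects, reached only if all 32 are women who could be pregnant, plus one for each woman turned away at Week 0. Up to 40 − 32 = 8 further consented subjects could replace those turned away, if they pass screening. One missed Week 4 challenge is 1/16 = 6.25% of that arm's Week 4 thermography.

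**What cannot be computed.** The documents give neither a pregnancy rate nor the number of women who could be pregnant, so no number of affected subjects is estimated.

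**The case against.** The strongest reply is that nothing is shown to follow. The protocol gives no reason for the exclusion and states no maternal or fetal hazard. The device is described as already cleared for headache in adults, home use is 8 minutes a day, and the immersion lasts one minute at 15°C. No endpoint or error rate is affected. This stands, and it keeps the point minor. It does not remove the gap, because the exclusion is the sponsor's own and is not verified when exposure starts.

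Second, the visit paragraphs are not full procedure lists. The Week -4 paragraph does not mention the dipstick either, so silence at later visits is weak evidence. That is fair, but the Study population section names screening and no other time.

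Third, the investigator may exclude anyone at unacceptable risk, and Weeks 1 and 2 give a subject the chance to speak up. But the discretion clause sits among the entry criteria, and discretion needs information that no step after Week -4 is scheduled to supply.

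Two stronger readings are tempting. A reader might infer that subjects receive no instruction about pregnancy at all. The documents do not support this: the consent pages were not part of the text reviewed and may contain one. Such an instruction would still depend on the subject knowing she is pregnant.

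A reader might also infer that finger ulcers and metallic neck implants need a scheduled re-check. The implant criterion is already worded as a bar on using the device, and the hands are imaged at each challenge visit. The Background section links Raynaud's phenomenon itself to digital ulceration. Withholding the Week 4 challenge for a new ulcer could therefore remove data from the subjects doing worst, possibly unequally by arm, and the Statistical analysis section gives no missing-data method.

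**Conclusion.** The point holds as a cheap improvement of minor severity. The only scheduled pregnancy test is 28, 56 and 84 days old at Weeks 0, 4 and 8, and the protocol text reviewed has neither a repeat test nor a pregnancy hold rule. Even if pregnancy is read purely as an entry criterion, enrolment and randomisation take place at Week 0, so entry itself rests on a 28-day-old result.

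The conclusion assumes that visits fall on their nominal weeks and that the screening-only wording is followed literally. It does not claim that any subject would be harmed, that any given number would be affected, or that the trial's inference would suffer.

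**What to change.** Amend the Study population section and the visit schedule as follows, for women who could be pregnant:

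1. **Week 0:** repeat the urine dipstick before randomisation. If it is positive, do not randomise.
2. **Weeks 4 and 8:** repeat it before stimulation. If it is positive, stop stimulation, do not switch the subject to gammaCore, continue the diary, and keep her in her randomised arm for analysis.
3. **Device training:** the protocol already plans this at Week 0 ("Prior to cold challenge subjects will be trained on proper usage and administration of sham and gammaCore devices") and again at Week 4 ("All subjects will be retrained on proper usage and administration of gammaCore"). At both, tell subjects to stop home use and call the site if they become pregnant, unless the consent form already says so.

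The rule is the same in both arms, so applying it does not require revealing allocation.

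The cost is a short amendment and the dipsticks counted above, with no new visit. An occasional challenge will be missed, at 1 of 16 of an arm's results each time at Week 4. The fix is partial: most stimulation happens at home, and for up to 28 days between tests it would still depend on self-report.
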